19.1.8 Key Secondary Outcome Analyses

Table 42: Summary of Days to First XR-NTX Injection by Induction Procedure

Induction Procedure	Days to First Injection While on the Unit		Results		
			Hazard Ratio	95% Lower Confidence Limit	95% Upper Confidence Limit
Rapid	N	N	X.xx	X.xx	X.xx
	Mean	X.X			
	SD	X.xx			
	Minimum	X			
	25th Percentile	X.X			
	Median	X.X			
	75th Percentile	X.X			
	Maximum	X			
Standard	N	N			
	Mean	X.X			
	SD	X.xx			
	Minimum	X			
	25th Percentile	X.X			
	Median	X.X			
	75th Percentile	X.X			
	Maximum	X			
Total	N	N			
	Mean	X.X			
	SD	X.xx			
	Minimum	X			
	25th Percentile	X.X			
	Median	X.X			
	75th Percentile	X.X			
	Maximum	X			

Table 43: Summary of Average Daily Opioid Withdrawal and Craving Scores by Induction Procedure

		Standard Procedure (N=XX)					Rapid Procedure (N=XX)					Total (N=XX)				
Inpatient Day		Daily Maximum COWS ¹	Daily COWS ¹	Daily SOWS ²	Daily Craving ³	Maxi-mum Craving in the past 24 Hours ⁴	Daily Maximum COWS ¹	Daily COWS ¹	Daily SOWS ²	Daily Craving ³	Maxi-mum Craving in the past 24 Hours ⁴	Daily Maximum COWS ¹	Daily COWS ¹	Daily SOWS ²	Daily Craving ³	Maxi-mum Craving in the past 24 Hours ⁴
Day 1	N (%)	N (X.x%)														
	Mean (SD)	X.x (X.xx)														
Day 2	N (%)															
	Mean (SD)															
Day 3	N (%)															
	Mean (SD)															
Day 4	N (%)															
	Mean (SD)															
Day #	N (%)															
	Mean (SD)															

¹ Clinical Opiate Withdrawal Scale ranging from 0-48.

² Subjective Opioid Withdrawal Scale ranging from 0-64.

³ Visual Analog Scale for question "Think about your craving for opioids. How intense is it right now?" ranging from 0-100.

⁴ Visual Analog Scale for question "Think about your desire to use opioids in the past 24 hours. How intense was your strongest desire to use? ranging from 0-100.

[figure not shown]

Figure 10: Average Daily Maximum COWS Score by Induction Procedure

Example figure provided.

[figure not shown]

Figure 6: Average Daily COWS Score by Induction Procedure

Example figure provided.

[figure not shown]

Figure 7: Average Daily SOWS Score by Induction Procedure

Example figure provided.

[figure not shown]

Figure 8: Average Daily VAS Craving Score at Time of Assessment by Induction Procedure

Example figure provided.

[figure not shown]

Figure 9: Average Daily Maximum VAS Craving Score within 24 Hours by Induction Procedure

Example figure provided.

Table 44: Summary of Average Opioid Withdrawal and Craving Scores by Procedure Phase and Induction Procedure

		Standard Procedure (N=XX)					Rapid Procedure (N=XX)					Total (N=XX)				
Procedure Phase		Daily Maximum COWS ¹	Daily COWS ¹	Daily SOWS ²	Daily Craving ³	Maximum Craving in the past 24 Hours ⁴	Daily Maximum COWS ¹	Daily COWS ¹	Daily SOWS ²	Daily Craving ³	Maximum Craving in the past 24 Hours ⁴	Daily Maximum COWS ¹	Daily COWS ¹	Daily SOWS ²	Daily Craving ³	Maximum Craving in the past 24 Hours ⁴
Pre-Buprenorphine	Participants with at least one score	N (X.x%)														
	N	N														
	Mean (SD)	X.x (X.xx)														
Buprenorphine	Participants with at least one score	N (X.x%)														
	N	N														
	Mean (SD)	X.x (X.xx)														
Post - Buprenorphine	Participants with at least one score	N (X.x%)														
	N	N														
	Mean (SD)	X.x (X.xx)														
Day of XR-NTX Injection Success	Participants with at least one score	N (X.x%)														
	N	N														
	Mean (SD)	X.x (X.xx)														

Table 44: Summary of Average Opioid Withdrawal and Craving Scores by Procedure Phase and Induction Procedure

		Standard Procedure (N=XX)					Rapid Procedure (N=XX)					Total (N=XX)				
Procedure Phase		Daily Maximum COWS ¹	Daily COWS ¹	Daily SOWS ²	Daily Craving ³	Maximum Craving in the past 24 Hours ⁴	Daily Maximum COWS ¹	Daily COWS ¹	Daily SOWS ²	Daily Craving ³	Maximum Craving in the past 24 Hours ⁴	Daily Maximum COWS ¹	Daily COWS ¹	Daily SOWS ²	Daily Craving ³	Maximum Craving in the past 24 Hours ⁴
Pre XR-NTX injection ⁵	Participants with at least one score	N (X.x%)														
	N	N														
	Mean (SD)	X.x (X.xx)														
Post XR-NTX Injection ⁵	Participants with at least one score	N (X.x%)														
	N	N														
	Mean (SD)	X.x (X.xx)														
Day of XR-NTX Injection Failure	Participants with at least one score	N (X.x%)														
	N	N														
	Mean (SD)	X.x (X.xx)														
Did Not Receive Buprenorphine	Participants with at least one score	N (X.x%)														
	N	N														
	Mean (SD)	X.x (X.xx)														

¹ Clinical Opiate Withdrawal Scale ranging from 0-48.

² Subjective Opioid Withdrawal Scale ranging from 0-64.

³ Visual Analog Scale for question "Think about your craving for opioids. How intense is it right now?" ranging from 0-100.

⁴ Visual Analog Scale for question "Think about your desire to use opioids in the past 24 hours. How intense was your strongest desire to use?" ranging from 0-100.

⁵ Only included if time of assessment collected on form. Percentage was calculated based on the number of participants who received XR-NTX injection.

[figure not shown]

Figure 10: Average Daily Maximum COWS Score by Induction Procedure and Phase

Example figure provided.

[figure not shown]

Figure 11: Average Daily COWS Score by Induction Procedure and Phase

Example figure provided.

[figure not shown]

Figure 12: Average Daily SOWS Score by Induction Procedure and Phase

Example figure provided.

[figure not shown]

Figure 13: Average VAS Craving Score at Time of Assessment by Induction Procedure and Phase

Example figure provided.

[figure not shown]

Figure 14: Average Maximum VAS Craving Score within 24 Hours by Induction Procedure and Phase

Example figure provided.

Table 45: Summary of Average Opioid Withdrawal and Craving in Standard Procedure by Procedure Phase

(N=XX)						
Procedure Phase		Daily Maximum COWS ¹	Daily COWS ¹	Daily SOWS ²	Daily Craving ³	Maximum Craving in the past 24 Hours ⁴
Pre-Buprenorphine	Participants with at least one score	N (X.x%)				
	N	N				
	Mean (SD)	X.x (X.xx)				
Buprenorphine Taper	Participants with at least one score	N (X.x%)				
	N	N				
	Mean (SD)	X.x (X.xx)				
Buprenorphine Washout	Participants with at least one score	N (X.x%)				
	N	N				
	Mean (SD)	X.x (X.xx)				
Day of XR-NTX Injection Success	Participants with at least one score	N (X.x%)				
	N	N				
	Mean (SD)	X.x (X.xx)				
Pre XR-NTX injection ⁵	Participants with at least one score	N (X.x%)				
	N	N				
	Mean (SD)	X.x (X.xx)				
Post XR-NTX Injection ⁵	Participants with at least one score	N (X.x%)				
	N	N				
	Mean (SD)	X.x (X.xx)				

Table 45: Summary of Average Opioid Withdrawal and Craving in Standard Procedure by Procedure Phase

(N=XX)					
Procedure Phase		Daily Maximum COWS ¹	Daily COWS ¹	Daily SOWS ²	Maximum Craving in the past 24 Hours ⁴
Day of XR-NTX Injection Failure	Participants with at least one score	N (X.x%)			
	N	N			
	Mean (SD)	X.x (X.xx)			

¹ Clinical Opiate Withdrawal Scale ranging from 0-48.

² Subjective Opioid Withdrawal Scale ranging from 0-64.

³ Visual Analog Scale for question "Think about your craving for opioids. How intense is it right now?" ranging from 0-100.

⁴ Visual Analog Scale for question "Think about your desire to use opioids in the past 24 hours. How intense was your strongest desire to use?" ranging from 0-100.

⁵ Only included if time of assessment collected on form. Percentage was calculated based on the number of participants who received XR-NTX injection.

[figure not shown]

Figure 15: Average Daily Maximum COWS Score in Standard Procedure by Phase

Example figure provided.

[figure not shown]

Figure 16: Average Daily COWS Score in Standard Procedure by Phase

Example figure provided.

[figure not shown]

Figure 17: Average Daily SOWS Score in Standard Procedure by Phase

Example figure provided.

[figure not shown]

Figure 18: Average VAS Craving Score at Time of Assessment in Standard Procedure by Phase

Example figure provided.

[figure not shown]

Figure 19: Average Maximum VAS Craving Score within 24 Hours in Standard Procedure by Phase

Example figure provided.

Table 46: Summary of Average Opioid Withdrawal and Craving in Rapid Procedure by Procedure Phase

(N=XX)					
Procedure Phase		Daily Maximum COWS ¹	Daily COWS ¹	Daily SOWS ²	Daily Craving ³
Pre-Buprenorphine	Participants with at least one score	N (X.x%)			
	N	N			
	Mean (SD)	X.x (X.xx)			
Buprenorphine Taper	Participants with at least one score	N (X.x%)			
	N	N			
	Mean (SD)	X.x (X.xx)			
Buprenorphine Washout	Participants with at least one score	N (X.x%)			
	N	N			
	Mean (SD)	X.x (X.xx)			
Low Naltrexone Titration	Participants with at least one score	N (X.x%)			
	N	N			
	Mean (SD)	X.x (X.xx)			
Naltrexone Day 1	Participants with at least one score	N (X.x%)			
	N	N			
	Mean (SD)	X.x (X.xx)			
Naltrexone Day #	Participants with at least one score	N (X.x%)			
	N	N			

Table 46: Summary of Average Opioid Withdrawal and Craving in Rapid Procedure by Procedure Phase

(N=XX)					
Procedure Phase		Daily Maximum COWS ¹	Daily COWS ¹	Daily SOWS ²	Daily Craving ³
	Mean (SD)	X.x (X.xx)			
Day of XR-NTX Injection Success	Participants with at least one score	N (X.x%)			
	N	N			
	Mean (SD)	X.x (X.xx)			
Pre XR-NTX injection ⁵	Participants with at least one score	N (X.x%)			
	N	N			
	Mean (SD)	X.x (X.xx)			
Post XR-NTX Injection ⁵	Participants with at least one score	N (X.x%)			
	N	N			
	Mean (SD)	X.x (X.xx)			
Day of XR-NTX Injection Failure	Participants with at least one score	N (X.x%)			
	N	N			
	Mean (SD)	X.x (X.xx)			

¹ Clinical Opiate Withdrawal Scale.

² Subjective Opioid Withdrawal Scale.

³ Visual Analog Scale for question "Think about your craving for opioids. How intense is it right now?"

⁴ Visual Analog Scale for question "Think about your desire to use opioids in the past 24 hours. How intense was your strongest desire to use?"

⁵ Only included if time of assessment collected on form. Percentage was calculated based on the number of participants who received XR-NTX injection.

[figure not shown]

Figure 20: Average Daily Maximum COWS Score in Rapid Procedure by Phase

Example figure provided.

[figure not shown]

Figure 21: Average Daily COWS Score in Rapid Procedure by Phase

Example figure provided.

[figure not shown]

Figure 22: Average Daily SOWS Score in Rapid Procedure by Phase

Example figure provided

[figure not shown]

Figure 23: Average VAS Craving Score at Time of Assessment in Rapid Procedure by Phase

Example figure provided.

[figure not shown]

Figure 24: Average Maximum VAS Craving Score within 24 Hours in Rapid Procedure by Phase

Example figure provided.

Table 47: Covariate Adjusted Modeling Results for Opioid Withdrawal as Measured by COWS and SOWS During the Induction Phase

Effects	COWS Daily Maximum				COWS Daily Average				SOWS			
	Odds ¹ Ratio	95% Lower Confidence Limit	95% Upper Confidence Limit	p-value	Odds ² Ratio	95% Lower Confidence Limit	95% Upper Confidence Limit	p-value	Estimate	95% Lower Confidence Limit	95% Upper Confidence Limit	p-value
Rapid versus Standard	X.xx	X.xx	X.xx	0.xxx								
Inpatient day												
Nexus Recovery Center versus ADAPT												
Avery Road Treatment Center versus ADAPT												
Aspire Health Partners vs. ADAPT												
Gibson Recovery Center versus ADAPT												
Stony Brook Eastern Long Island Hospital versus ADAPT												

¹The odds of at least one moderate to severe daily COWS score (maximum score ≥ 12).

²The odds of presence of moderate to severe average daily COWS score (average score ≥ 12).

Table 48: Covariate Adjusted Modeling Results for Craving for Opioids During the Induction Phase								
Effects	Craving VAS at Time of Assessment				Maximum Craving VAS within 24 Hours			
	Estimate	95% Lower Confidence Limit	95% Upper Confidence Limit	p-value	Estimate	95% Lower Confidence Limit	95% Upper Confidence Limit	p-value
Rapid versus Standard	X.xx	X.xx	X.xx	0.xxx				
Inpatient day								
Nexus Recovery Center versus ADAPT								
Avery Road Treatment Center versus ADAPT								
Aspire Health Partners vs. ADAPT								
Gibson Recovery Center versus ADAPT								
Stony Brook Eastern Long Island Hospital versus ADAPT								

Table 49: Retention in the Study to Receive at Least One XR-NTX Injection after Induction Success

Induction Procedure	Number with Induction Success	At Least One Additional Injection Administered	Results			
			Odds Ratio	95% Lower Confidence Limit	95% Upper Confidence Limit	p-value
Rapid	N (X.x%)	N (X.x%)	X.xx	X.xx	X.xx	0.xxx
Standard						
Total						

19.1.9 Safety

Table 50: Summary of Serious Adverse Events by Induction Procedure			
	Induction Procedure		
	Standard (N=XX)	Rapid (N=XX)	Total (N=XX)
Number of participants with at least one serious adverse event (SAE) ¹	N (X.x%)		
Maximum severity of SAE for participants with at least one SAE ²			
Grade 1 - Mild	N (X.x%)		
Grade 2 - Moderate			
Grade 3 - Severe			
Number of participants with at least one SAE related to study medication ¹	N (X.x%)		
Number of participants diagnosed with COVID-19 ¹	N (X.x%)		
Number of SAEs	N		
Severity of SAEs ³			
Grade 1 - Mild	N (X.x%)		
Grade 2 - Moderate			
Grade 3 - Severe			
Relationship of SAE to study medication ³			
No	N (X.x%)		
Yes			

¹ The percentage was calculated based on the denominator of the number of enrolled participants.

² The percentage was calculated with the denominator as the number of enrolled participants with SAEs.

³ The percentage was calculated with the denominator as the number of SAEs.

Table 51: Summary of MedDRA-coded Serious Adverse Events by Induction Procedure

System Organ Class/Preferred Term (MedDRA V25.0)	Induction Procedure		
	Standard (N=XX)	Rapid (N=XX)	Total (N=XX)
Participants with at least one serious adverse event (SAE)	N (x.x%)		
Injury, poisoning and procedural complications	N (x.x%)		
Overdose	N (x.x%)		
Road traffic accident			
Psychiatric disorders			
Suicidal ideation			
Respiratory, thoracic and mediastinal disorders			
Chronic obstructive pulmonary disease			
Nervous system disorders			
Depressed level of consciousness			
Metabolism and nutrition disorders			
Hypokalaemia			

Percentages were calculated based on the number of participants experiencing the adverse event at least once as the numerator and the number of participants enrolled as the denominator.

Example SOC and preferred terms provided.

Table 52: Summary of Targeted Safety Events by Study Phase and Induction Procedure

Study Phase		Induction Procedure		Total (N=XX)	p-Value ⁸
		Standard (N=XX)	Rapid (N=XX)		
Overall	Number of participants with at least one targeted safety event (TSE) ¹				
	Number of participants with at least one TSE of the following types ²				
	Fall event ³				
	Acute change in mental status ⁴				
	Acute medical complication likely exacerbated by the stress of withdrawal ⁵				
	Acute psychiatric symptoms ⁶				
	Number of participants with at least one TSE related to study medication ¹				
	Number of participants with at least one TSE defined as serious adverse event ¹				
	Number of TSEs				
	Type of TSE ⁷				
	Fall event ³				
	Acute change in mental status ⁴				
	Acute medical complication likely exacerbated by the stress of withdrawal ⁵				
	Acute psychiatric symptoms ⁶				
	Relationship of TSE to study medication ⁷				
	No				
	Yes				
	TSE defined as serious adverse event ⁷				
	No				
	Yes				

Table 52: Summary of Targeted Safety Events by Study Phase and Induction Procedure

Study Phase		Induction Procedure		Total (N=XX)	p-Value ⁸
		Standard (N=XX)	Rapid (N=XX)		
Screening Phase	Number of participants with at least one targeted safety event (TSE) ¹	N (X.x%)			
	Number of participants with at least one TSE of the following types ²				
	Fall event ³	N (X.x%)			
	Acute change in mental status ⁴				
	Acute medical complication likely exacerbated by the stress of withdrawal ⁵				
	Acute psychiatric symptoms ⁶				
	Number of participants with at least one TSE related to study medication ¹	N (X.x%)			
	Number of participants with at least one TSE defined as serious adverse event ¹	N (X.x%)			
	Number of TSEs	N			
	Type of TSE ⁷				
	Fall event ³	N (X.x%)			
	Acute change in mental status ⁴				
	Acute medical complication likely exacerbated by the stress of withdrawal ⁵				
	Acute psychiatric symptoms ⁶				
	Relationship of TSE to study medication ⁷				
	No	N (X.x%)			
	Yes				
	TSE defined as serious adverse event ⁷				
	No	N (X.x%)			
	Yes				

Table 52: Summary of Targeted Safety Events by Study Phase and Induction Procedure

Study Phase	Induction Procedure			
	Standard (N=XX)	Rapid (N=XX)	Total (N=XX)	p-Value⁸
Induction Phase	Number of participants with at least one targeted safety event (TSE) ¹	N (X.x%)		
	Number of participants with at least one TSE of the following types ²			
	Fall event ³	N (X.x%)		
	Acute change in mental status ⁴			
	Acute medical complication likely exacerbated by the stress of withdrawal ⁵			
	Acute psychiatric symptoms ⁶			
	Number of participants with at least one TSE related to study medication ¹	N (X.x%)		
	Number of participants with at least one TSE defined as serious adverse event ¹	N (X.x%)		
	Number of TSEs	N		
	Type of TSE ⁷			
	Fall event ³	N (X.x%)		
	Acute change in mental status ⁴			
	Acute medical complication likely exacerbated by the stress of withdrawal ⁵			
	Acute psychiatric symptoms ⁶			
	Relationship of TSE to study medication ⁷			
	No	N (X.x%)		
	Yes			
	TSE defined as serious adverse event ⁷			
	No	N (X.x%)		
	Yes			

Table 52: Summary of Targeted Safety Events by Study Phase and Induction Procedure

Study Phase	Induction Procedure			
	Standard (N=XX)	Rapid (N=XX)	Total (N=XX)	p-Value⁸
Post-Induction Phase	Number of participants with at least one targeted safety event (TSE) ¹	N (X.x%)		
	Number of participants with at least one TSE of the following types ²			
	Fall event ³	N (X.x%)		
	Acute change in mental status ⁴			
	Acute medical complication likely exacerbated by the stress of withdrawal ⁵			
	Acute psychiatric symptoms ⁶			
	Number of participants with at least one TSE related to study medication ¹	N (X.x%)		
	Number of participants with at least one TSE defined as serious adverse event ¹	N (X.x%)		
	Number of TSEs	N		
	Type of TSE ⁷			
	Fall event ³	N (X.x%)		
	Acute change in mental status ⁴			
	Acute medical complication likely exacerbated by the stress of withdrawal ⁵			
	Acute psychiatric symptoms ⁶			
	Relationship of TSE to study medication ⁷			
	No	N (X.x%)		
	Yes			
	TSE defined as serious adverse event ⁷			
	No	N (X.x%)		
	Yes			

¹ The percentage was calculated based on the denominator of the number of enrolled participants.

² The percentage was calculated with the denominator as the number of participants with TSEs.

³ Likely related to medical/psychiatric condition such as dizziness, confusion with head injury.

⁴ Disorientation, amnesia, cerebrovascular accident, coma.

⁵ Hypertensive crisis, hypotensive event with medical sequelae such as fall and/or requiring urgent fluid resuscitation, severe chest pain, cardiac arrhythmia, acute respiratory decompensation, asthma attack, diabetic ketoacidosis, severe hypoglycemia.

⁶Acute psychiatric symptoms (i.e., psychosis, hypomania, severe agitation, violence).

⁷The percentage was calculated with the denominator as the number of TSEs.

⁸p-value is from Fisher's Exact Test.

Table 53: Summary of Study Injection Site Examinations

	Induction Procedure		
	Standard (N=XX)	Rapid (N=XX)	Total (N=XX)
Number of participants with at least one abnormal injection site ¹	N (X.x%)		
Number of abnormal injection sites	N		
Symptom experienced ²			
None	N (X.x%)		
Pain			
Tenderness			
Erythema/Redness			
Swelling			
Induration			
Abscess			
Necrosis			
Bruising			
Pruritus			
Nodule			
Hematoma			
Sterile abscess			
Cellulitis			
Warmth			
Other			
Severity ²			
Grade 1 - Mild	N (X.x%)		
Grade 2 - Moderate			
Grade 3 - Severe			

¹ Percentages were calculated based on number of enrolled participants.

² Percentages were calculated based on number of abnormal injection sites.

Table 54: Summary of Non-Fatal Opioid Overdoses by Study Phase and Induction Procedure

Study Phase		Induction Procedure		Total (N=XX)
		Standard (N=XX)	Rapid (N=XX)	
Baseline (i.e., before enrollment in the study)	Number of participants with at least one overdose	N (X.x%)		
	Receive NARCAN (naloxone) at home to reverse overdose ^{1,2}			
	No	N (X.x%)		
	Yes			
	Overdose resulting in hospitalization ^{1,2}			
	No	N (X.x%)		
	Yes			
	Before the overdose, how likely was it that you would overdose ^{2,3}			
	N	N		
	Mean	X.X		
	SD	X.XX		
	Minimum	X		
	25th Percentile	X.X		
	Median	X		
	75th Percentile	X.X		
	Maximum	X		
	Before the overdose, how strongly did you want to die ^{2,3}			
	N	N		
	Mean	X.X		
	SD	X.XX		
	Minimum	X		
	25th Percentile	X.X		
	Median	X		
	75th Percentile	X.X		
	Maximum	X		
	At the time of the overdose, were you trying to kill yourself ^{2,4}			
	N	N		
	Mean	X.X		
	SD	X.XX		
	Minimum	X		

Table 54: Summary of Non-Fatal Opioid Overdoses by Study Phase and Induction Procedure

Study Phase		Induction Procedure		Total (N=XX)
		Standard (N=XX)	Rapid (N=XX)	
	25th Percentile	X.X		
	Median	X		
	75th Percentile	X.X		
	Maximum	X		
	How likely would you be to seek out certain opioids that resulted in fatal overdoses in your area ⁵			
	N	N		
	Mean	X.X		
	SD	X.XX		
	Minimum	X		
	25th Percentile	X.X		
	Median	X		
	75th Percentile	X.X		
	Maximum	X		

Table 54: Summary of Non-Fatal Opioid Overdoses by Study Phase and Induction Procedure

Study Phase		Induction Procedure		Total (N=XX)
		Standard (N=XX)	Rapid (N=XX)	
Day 1 to Day 28 Post-Induction Period	Number of participants with at least one overdose	N (X.x%)		
	Receive NARCAN (naloxone) at home to reverse overdose ^{1,2}			
	No	N (X.x%)		
	Yes			
	Overdose resulting in hospitalization ^{1,2}			
	No	N (X.x%)		
	Yes			
	Before the overdose, how likely was it that you would overdose ^{2,3}			
	N	N		
	Mean	X.X		
	SD	X.XX		
	Minimum	X		
	25th Percentile	X.X		
	Median	X		
	75th Percentile	X.X		
	Maximum	X		
	Before the overdose, how strongly did you want to die ^{2,4}			
	N	N		
	Mean	X.X		
	SD	X.XX		
	Minimum	X		
	25th Percentile	X.X		
	Median	X		
	75th Percentile	X.X		
	Maximum	X		
	At the time of the overdose, were you trying to kill yourself ^{2,5}			
	N	N		
	Mean	X.X		
	SD	X.XX		
	Minimum	X		

Table 54: Summary of Non-Fatal Opioid Overdoses by Study Phase and Induction Procedure

Study Phase		Induction Procedure		Total (N=XX)

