16.11 Safety Analysis

SAEs will be summarized by body system and preferred term using MedDRA codes (per The Medical Dictionary for Regulatory Activities). Targeted Safety Events (TSEs) will be coded if feasible. For a list of TSEs refer to Section 12.3.10. TSEs and SAEs will be presented as: (1) the number and proportion of participants experiencing at least one incidence of each event overall; and (2) the total number of each event overall in tabular form. Listings of SAEs will be sorted by

system organ class (SOC), and preferred term (PT). Detail in these listings will include severity, relationship to study medication(s), and action taken, as available.

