10.2 Serious Adverse Events

Serious adverse events (SAEs) are defined in Section 3.2.8. SAEs will be summarized by presenting the number of events, number of participants experiencing SAEs, and the relatedness and type of SAEs by induction procedure.

All SAEs will be coded using MedDRA® dictionary version v25.0. The number and proportion of participants experiencing SAE will be provided by induction procedure and overall. SAEs will be summarized by System Organ Class (SOC) and Preferred Term (PT). The proportion will be calculated as the number of participants who experience the event at least once divided by the number of participants in the induction procedure or overall. Proportions will be calculated at the preferred term level, at the SOC level, and for participants with at least one SAE. If a participant experiences multiple episodes of an event, then the event is only counted once. Detailed listings of SAEs by induction procedure will be provided. The listing will include Participant ID, date of IC, date of enrollment, SAE onset date, description, severity of AE, relatedness to study medication, outcome, resolution date, reason reported as SAE, and MedDRA® coded preferred term and system organ class. Narratives for all serious adverse events will be provided.

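### SAP Table 52 reports each targeted-safety-event type as a share of participants who had any such event, not as a proportion of participants at risk

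*SAP*

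**What the plan says.** SAP 19.1.9, Table 52, summarises TSEs by procedure in four blocks: Overall, Screening, Induction and Post-Induction. In each block the row "Number of participants with at least one TSE of the following types" covers falls, mental-status change, withdrawal-related medical complications and psychiatric symptoms, and it carries footnote 2: "The percentage was calculated with the denominator as the number of participants with TSEs".

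The other participant-level rows of the table (any TSE, TSE related to study medication, TSE that is also serious) carry footnote 1: "The percentage was calculated based on the denominator of the number of enrolled participants". A second set of type rows counts events, and footnote 7 divides those by the number of TSEs.

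Elsewhere the documents read differently:

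- Protocol 16.11: "TSEs and SAEs will be presented as: (1) the number and proportion of participants experiencing at least one incidence of each event overall".
- SAP 10.2, on serious adverse events: the count of participants with the event is "divided by the number of participants in the induction procedure or overall".
- SAP Table 51, on coded serious adverse event terms: "the number of participants enrolled as the denominator".

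SAP 10.1 sets no denominator for TSE types. It names Fisher's exact test for comparing the procedures without defining the table to be tested, and footnote 8 of Table 52 adds nothing on this.

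**The concern.** Table 52 compares two procedures, and its type rows are where a reader looks for the risk of a fall or a mental-status change under each. A percentage whose denominator is participants with any TSE does not answer that question, because it moves with the frequency of the other TSE types. No other row gives the type-specific risk, since the second set of type rows divides by events.

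TSEs are among the key secondary outcomes (SAP 8.4), with a stated hypothesis of equivalent rates (SAP Table 5). The protocol also names more severe precipitated withdrawal and side effects of standing adjunctive medication as possible risks of the Rapid Procedure (4.1.2), and precipitated withdrawal is itself listed within one TSE type (SAP 3.2.6). If such events were more common under the Rapid Procedure, they would enlarge its footnote 2 denominator and lower its printed percentages for the other three types.

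**Working it through.** Table 52 is an empty shell and neither document gives a TSE rate, so there is no figure to reproduce. The check is algebra followed by illustrations on assumed counts.

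**Formula.** Let n be the number of participants in a procedure, p the risk of at least one TSE of a given type, and q the risk of at least one TSE of any type.

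- Footnote 2 prints (n × p) / (n × q) = p/q.
- An all-participant denominator prints (n × p) / n = p.
- The printed Rapid/Standard ratio is therefore (p_RP / p_SP) × (q_SP / q_RP). At equal p it reduces to q_SP / q_RP, so the procedure with more participants having any TSE prints the lower figure. If q is equal in the two procedures, the ratio is undistorted and only the level changes.

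**Range at equal risk.** Assume p = 4% in both procedures and q_SP = 10%. The Standard cell prints 4/10 = 40.0%. The Rapid cell prints:

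- 40.0% if q_RP = 10%
- 26.7% if q_RP = 15%
- 20.0% if q_RP = 20%
- 13.3% if q_RP = 30%

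**Worked counts.** All event counts are assumed. Cases A and B use the planned 225 per procedure (Protocol 8.0). Cases C and D use the arm sizes shown in SAP Table 55, 190 and 225. Each pair is Standard v Rapid.

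| Case | Any TSE | Falls | Printed under footnote 2 | Over all in the procedure |
|---|---|---|---|---|
| A | 11 v 27 | 7 v 7 | 7/11 = 63.6% v 7/27 = 25.9% | 7/225 = 3.1% v 3.1% |
| B | 11 v 27 | 7 v 11 | 63.6% v 11/27 = 40.7% | 3.1% v 11/225 = 4.9% |
| C | 19 v 45 | 8 v 9 | 8/19 = 42.1% v 9/45 = 20.0% | 8/190 = 4.2% v 9/225 = 4.0% |
| D | 19 v 45 | 8 v 18 | 42.1% v 18/45 = 40.0% | 4.2% v 18/225 = 8.0% |

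In A and C near-equal risks print as a large difference. In B the order of the printed percentages is the reverse of the risks. In D a near-doubling prints as near equality.

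**Fisher's exact test.** The SAP does not say which 2x2 table is tested. If the by-type test followed footnote 2, p would be 0.12 in case C and 1.00 in case D. On all participants it would be 1.00 and 0.15.

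**The case against.** The strongest reply is that nothing is lost. The cells are laid out as a count with a percentage, the arm size stands in the column header, and the row above the type rows gives participants with any TSE over those enrolled. In case A the reader would see 7 and 7 under headers of 225 and could recover 3.1% in one division. Every TSE is also listed individually by procedure. This stands, and it limits the consequence to the printed percentage.

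It can also be said that footnote 2 openly describes a nested breakdown, as Table 50 does for maximum severity among participants with serious adverse events. As a description of case mix that is legitimate. It does not supply what Protocol 16.11 asks for. That section names no denominator, but a proportion of participants experiencing each event is most naturally read as being over all participants. SAP 10.2 and Table 51 govern serious adverse events only, so they show inconsistency of practice rather than a broken rule.

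Three stronger readings are tempting, and the documents do not support them:

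- A reader might infer that the table will conceal or reverse a safety signal. That needs unequal any-TSE risks, and the documents give none. More severe withdrawal under the Rapid Procedure is raised only as a possibility, and the stated hypothesis is equivalence. Even then the counts remain visible.
- A reader might infer that Fisher's test is run on the wrong denominator. Nothing ties the test to footnote 2; the tested table is simply undefined.
- A reader might infer that repeated events in one person drive the effect. The denominator counts participants, so repeats do not change it.

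**Conclusion.** The point holds as a reporting inconsistency of minor severity. Footnote 2 makes the type-specific percentages p/q rather than p, which departs from the natural reading of Protocol 16.11 and from the treatment of serious adverse event terms. That much follows from the text and the algebra alone.

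The size is not known. It depends on how far any-TSE risk differs between the procedures, and every count above is an assumption. If any-TSE risk is equal, the comparison between procedures is unaffected and only the level of each percentage is misleading. The key secondary outcomes are not intended to be confirmatory (SAP 11.0), and no primary conclusion or decision rule depends on these cells.

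Moving footnote 2 to the footnote 1 wording would not settle the matter. Footnote 1 divides by enrolled participants, while SAP 3.1.4 defines the safety population as everyone who signs consent, SAP 10.0 analyses safety on that population, and SAP 18.0 lists the TSE summary under it. The difference matters most in the Screening block, where an event can precede enrolment.

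**What to change.** - In all four blocks of Table 52, give the type rows the same participants-at-risk denominator as the row for at least one TSE.
- Decide whether that denominator is enrolled participants or the SAP 3.1.4 safety population. Word footnote 1 and SAP 10.1 to match, with an explicit rule for the Screening block, including how consented participants who never enrol are assigned to a procedure.
- State in SAP 10.1 and footnote 8 that the by-type Fisher's exact test compares participants with and without that type on this denominator.
- If the share among TSE participants is wanted, keep it as a separate row labelled as descriptive.

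The cost is a change to the footnotes, a sentence or two in SAP 10.1 and an edit to the table program. No new data are needed.
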